#### ISIS 703802-CS5

CONFIDENTIAL

Amendment 1

16 February 2018

Protocol

# Appendix ASchedule of Procedures Continued

	Scree	ning		Treatment Period					Follow-up Period				
	Run-in #	Qual †											
Study Week	-6 to -1	-1 to 0	1	5	9	13	17	21	25	27/ET	4*	8*	13*
Study Day	-42 to -1	-7 to -1	1	29	57	85	113	141	169	183		from the ment pe	e end of riod o
Visit and Testing Window +/- Days	0	0	0	2	2	2	3	3	3	0	3	3	3
Hematology	Х			-		EVERY 14 D	DAYS (+/- 2	days) f			X h	X h	X h
Coagulation	Х		Х							Х			
Hepatitis B, C, HIV	Х												
Thyroid Panel	Х												
Inflammatory			Х			Х				Х			Х
Liver Biomarkers			Х			Х				Х			Х
Plasma PK - ISIS 703802 I			X 	X 	X 	X 	X 	X 	X 	Х	Х	Х	Х
Anti-ISIS 703802 Antibodies			Х	Х	Х	Х		Х		Х		Х	Х
FSH (women only, if applicable) j, m	Х												
Serum Pregnancy Test m	Х		Х	Х	Х	Х	Х	Х	Х	Х	Х	Х	
Archived Serum & Plasma Samples $_{j,n}$			х		х		х			Х			х
PD Panel j	Х	Х	Х	Х	Х	Х	Х	Х	Х	Х	Х	Х	Х
Extended Lipid Panel j	Х	Х	Х	Х	Х	Х	Х	Х	Х	Х	Х	Х	Х
HbA1C j	Х		Х			Х				Х			Х
Quality of Life Assessment		Х				Х				Х			
Widespread Pain Diary		Х			TO E	BE DONE AT	OUTPATIE	ENT VISITS			Х	Х	Х
Study Drug: SC Injection			WEEK	WEEKLY SUBCUTANEOUS ADMINISTRATION OF STUDY DRUG (Week 1 through Week 26/Day 176)									
Adverse Events		TO BE COLLECTED FROM TIME OF INFORMED CONSENT TO END OF FOLLOW-UP PERIOD											
Concomitant Medication			TO BE (	COLLECTE	D FROM T	IME OF INFO	ORMED CC	NSENT TO	END OF FOLL	OW-UP PE	RIOD		

1010 / 00 002 00		
Protocol		16 February 2018
Appendix A	Schedule of Procedures Continued	

CONFIDENTIAL

Amendment 1

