The pharmacokinetics of ISIS 703802 evaluated in Study ISIS 703802-CS1 showed rapid absorption following SC administration, with median time to maximum plasma concentrations ( $T_{max}$ ) ranging from 1 to 6 hours. Similar  $T_{max}$  values were observed at all dose levels. After reaching  $C_{max}$ , plasma concentrations of ISIS 703802 declined in a multi-phasic fashion with a rapid disposition phase, followed by a slower elimination phase with terminal elimination half-life of 3 to 5 weeks. The peak ( $C_{max}$ ) and total exposure (AUC) after a single SC dose increased approximately dose proportionally from 20 to 40 mg, and greater than dose proportionally from 40 to 80 mg, suggesting more efficient tissue uptake at lower doses. After single and multiple SC doses in the range of 10 to 60 mg, the  $C_{max}$  and AUC increased

approximately dose proportionally. No accumulation based on  $C_{max}$  or AUC was observed after 6 weekly doses.

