# 3.4.3 Post-Treatment

Subjects are to return to the Study Center for follow-up visits. These visits will take place at 4, 8 and 13 weeks after the Treatment Period (last dose through one dosing interval post last dose). Refer to Schedule of Procedures in Appendix A.

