# 6.1.3 Post-Treatment Period

Each subject will be followed for safety assessments for 13 weeks after the Treatment Period (last dose through one dosing interval post last dose). During the post-treatment evaluation period, subjects will return to the Study Center for outpatient visits for safety and clinical laboratory evaluations.  $A \pm 3$ -day excursion from the scheduled visit date is permitted for this time period.

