# 6.3 Restriction on the Lifestyle of Subjects

# 6.3.1 Contraception Requirements

All male subjects and women of childbearing potential must refrain from sperm/egg donation and either be abstinent† or practice effective contraception from the time of signing the informed consent form until at least a period of 13 weeks after their last dose of study treatment.

Male subjects engaged in sexual relations with a female of child-bearing potential must also encourage their female partner to use effective contraception from the time of signing the informed consent until a period of 13 weeks after the subject's last dose of study treatment.

For the purposes of this study, women of childbearing potential are defined as any female who has experienced menarche, and who does not meet one of the following conditions:

- Postmenopausal: 12 months of spontaneous amenorrhea in females > 55 years of age or, in females ≤ 55 years, 12 months of spontaneous amenorrhea without an alternative medical cause and FSH levels in the postmenopausal range for the laboratory involved
- 6 weeks after surgical bilateral oophorectomy with or without hysterectomy
- Post hysterectomy

For the purposes of the study, effective contraception is defined as follows:

For male subjects:

- Effective male contraception includes a vasectomy with negative semen analysis at follow-up, or the use of condoms together with spermicidal foam/gel/film/ cream/suppository
- Male subjects with partners that are pregnant must use condoms as contraception to ensure that the fetus is not exposed to the Study Drug

For female subjects and female partners of male subjects:

- Using 2 of the following acceptable methods of contraception: surgical sterilization (e.g., bilateral tubal ligation), hormonal contraception, intrauterine contraception/device, or any 2 barrier methods (a combination of male or female condom\* with diaphragm, sponge, or cervical cap) together with spermicidal foam/gel/film/cream/suppository
- **†Note:** Abstinence is only acceptable as true abstinence, i.e., when this is in line with the preferred and usual lifestyle of the patient. Periodic abstinence (e.g., calendar, ovulation, symptothermal, post-ovulation methods), declaration of abstinence for the duration of a trial and withdrawal are not acceptable methods of contraception.

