#### 9.5.4 Contraception and Pregnancy

Subjects must continue to use appropriate contraception with their partners, or refrain from sexual activity, as described in Section 6.3.1. If a subject becomes pregnant or a pregnancy is suspected, or if a male subject makes or believes that he has made someone pregnant during the Study, then the Study Center staff must be informed immediately. An Initial Pregnancy Form should be submitted to the Sponsor or designee within 24 hours of first learning of the occurrence of pregnancy. Follow-up information including delivery or termination is reported by designating as 'Follow-up' on the Pregnancy Forms and reported within 24 hours. Payment for all aspects of obstetrical care, child or related care will be the subject's responsibility. Female subjects: If a suspected pregnancy occurs while on the Study (including follow-up), a pregnancy test will be performed. The subject with a confirmed pregnancy will be immediately withdrawn from treatment with Study Drug. However, the subject will be encouraged to complete the post-treatment follow-up portion of the Study to the extent that study procedures do not interfere with the pregnancy. Regardless of continued study participation, the study physician will assist the subject in getting obstetrical care and the progress of the pregnancy will be followed until the outcome

of the pregnancy is known (i.e., delivery, elective termination, or spontaneous abortion). If the pregnancy results in the birth of a child, the Study Center and Sponsor may require access to the mother and infant's medical records for an additional 8 weeks after birth. Follow-up will be performed to the extent permitted by the applicable regulations and privacy considerations. Male subjects: The progress of the pregnancy of a male subject's partner should be followed until the outcome of the pregnancy is known (i.e., delivery, elective termination, or spontaneous abortion). If the pregnancy results in the birth of a child, the Study Center and Sponsor may request access to the mother and infant's medical records for an additional 8 weeks after birth. Follow-up will be performed to the extent permitted by the applicable regulations and privacy considerations.

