- m Women who are not surgically sterile or post-menopausal.
- n Serum and plasma samples will be collected and stored for follow-up exploration of laboratory findings and/or AEs (e.g., measurement of cytokine and/or chemokine levels, measurement of additional markers of kidney function, measurement of antibodies, etc.) and will be retained until completion of the final study report.
- o Treatment period is defined as the time from the first dose through one dosing interval post last dose.
- p Genetic testing will only be performed for eligibility if there is no documented genetic testing in medical history.
- q 24-hour urine sample for creatinine clearance and protein should also be obtained in the event of an eGFR (CKD-EPI) value meeting criteria specified in Sections 8.5.2 and 8.6.2.

Time (time is in reference to Study Drug administration):

1 Pre-dose

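### The last scheduled pregnancy test falls four weeks before the required contraception period ends, and none is scheduled at the final visit

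*Combined protocol and SAP*

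**What the plan says.** Five places in Amendment 1 bear on this.

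- **Contraception (Section 6.3.1, and inclusion criterion 8 in Section 5.1).** Women of childbearing potential must be abstinent or use effective contraception "until at least a period of 13 weeks after their last dose of study treatment". For female subjects, effective contraception means two of the listed methods.
- **Dosing (Appendix A).** Weekly injections run "Week 1 through Week 26/Day 176".
- **Follow-up anchor (Section 3.4.3 and Appendix A footnote o).** "These visits will take place at 4, 8 and 13 weeks after the Treatment Period (last dose through one dosing interval post last dose"). Footnote o agrees: "Treatment period is defined as the time from the first dose through one dosing interval post last dose". Section 6.1.3 allows three days either side: a ±3-day "excursion from the scheduled visit date is permitted for this time period".
- **Scheduled tests (Appendix A).** The row "Serum Pregnancy Test m" has entries at screening, Weeks 1, 5, 9, 13, 17, 21, 25 and 27/ET, and follow-up Weeks 4 and 8. The follow-up Week 13 cell is empty. Footnote m limits the row to women who are neither surgically sterile nor past menopause.
- **For-cause tests (Section 9.5.4).** "If a suspected pregnancy occurs while on the Study (including follow-up), a pregnancy test will be performed". The site must be told at once, and a confirmed pregnancy is followed to its outcome whether or not the woman stays in the study.

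The protocol before Amendment 1 has the same empty cell, and none of the three administrative clarification letters changes the row.

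**The concern.** Section 6.3.1 marks out a post-dose period in which conception is to be avoided, and Section 9.5.4 sets up reporting and follow-up for any pregnancy that occurs. Scheduled testing feeds that system with pregnancies nobody has suspected. The protocol plainly does not rely on suspicion alone, since it tests at every treatment-period visit and at two follow-up visits. Yet the testing stops before the protected period does, although a later visit exists at which blood is drawn.

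At stake is case-finding for safety. Adverse event collection ends with follow-up (Sections 9.4.1 and 9.4.2). A pregnancy that neither the subject nor the site has recognised by the last visit therefore has no scheduled route into the reporting system. The efficacy analysis is not affected.

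**Working it through.** **Is the blank real?** The row has 13 cells, matching the 13 visit columns. Qualification and follow-up Week 13 are empty and the other 11 are marked. Neighbouring rows (archived samples, PD panel, lipid panel, HbA1c) do carry an entry at follow-up Week 13, so that column survived the text extraction.

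**Calendar.** The inputs are 26 weekly doses from Day 1, the footnote o definition of the treatment period, follow-up visits at 4, 8 and 13 weeks after it, and contraception to 13 weeks after the last dose.

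1. Last dose: 1 + 25 × 7 = Day 176. This reproduces the protocol's own figure.
2. End of treatment period: 176 + 7 = Day 183, the nominal day of the Week 27/ET visit.
3. Follow-up visits at 183 + 7w: Week 4 = Day 211, Week 8 = Day 239, Week 13 = Day 274. These are 5, 9 and 14 weeks after the last dose.
4. End of required contraception: 176 + 13 × 7 = Day 267.
5. Protected days after the last scheduled test: 267 − 239 = 28, which is 28/91 = 31% of the post-dose protected period.
6. With the ±3-day window the Week 8 test falls on Day 236 to 242, so the gap is 31 to 25 days.
7. Last scheduled test to last visit: 274 − 239 = 35 days (29 to 41 with both windows).

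The gap does not depend on completing all 26 doses. If the visits are counted from one dosing interval after the last dose, the last test is at 1 + 8 = 9 weeks and 13 − 9 = 4 weeks remain.

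**What a Week 13 test would recover.** The documents give no time from conception to a positive serum test. I assume 7, 10 or 14 days. A conception is missed if it occurs later than the test day minus that lag.

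| Assumed lag (days) | Protected days missed now: 267 − (239 − lag) | Protected days missed with a Day 274 test: max(0, 267 − (274 − lag)) |
|---|---|---|
| 7 | 35 | 0 |
| 10 | 38 | 3 |
| 14 | 42 | 7 |

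If the Week 13 visit is taken three days early (Day 271), the 14-day case becomes 267 − (271 − 14) = 10 days.

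**How likely is an event?** The documents give no conception rate. Assume 3 to 6 women under footnote m and an annual conception probability of 1% to 10%. The expected number over 28 days is then between 3 × 0.01 × 28/365 = 0.002 and 6 × 0.10 × 28/365 = 0.05.

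**The case against.** The strongest reply is that nothing is contradictory. Section 6.3.1 sets a contraception period, Appendix A sets a test schedule, and a site can follow both as written. No passage says routine tests must run as long as contraception. That stands: this is a gap in a schedule, not a conflict between rules.

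Section 9.5.4 also gives real protection. It covers follow-up, obliges the subject to tell the site, and follows a known pregnancy to its outcome. The Week 13 visit includes a physical examination and adverse event collection, and archived serum is drawn there. That stands too, and it narrows the gap to a pregnancy nobody suspects. The small sample and the two-method requirement make such an event improbable.

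Three stronger readings are tempting, and the documents do not support them.

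- A reader might infer that for-cause testing is weak here because irregular cycles are part of the disease. Polycystic ovary syndrome or similar symptoms are only one of five minor criteria, and a genetic diagnosis needs none of them. Nothing shows that an enrolled woman would have irregular cycles.
- A reader might turn the half-life ("followed by a slower elimination phase with terminal elimination half-life of 3 to 5 weeks") into a percentage of drug remaining at the last test. Section 2.3.4 describes a rapid disposition phase first and does not say how much the terminal phase contributes. Such a percentage would not show fetal exposure.
- A reader might conclude that late pregnancies would probably surface after the study and that the safety record would be wrong. The documents give no basis for that probability.

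**Conclusion.** The point holds as a modest gap in safety scheduling. Four weeks of the thirteen-week protected period (28 of 91 days; 25 to 31 with the window) have no scheduled pregnancy test after them, although the final visit comes 7 days after the period ends (274 − 267). An unsuspected pregnancy conceived in those weeks could leave the study undetected.

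The 28-day figure is strictly the distance from the last test to the end of contraception. The 35 days to the last visit are a different interval. A figure of five weeks or more for the protected period needs an assumed detection lag that is not in the documents.

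The table reading and the dates are firm. The chance of an event is small, about 0.002 to 0.05 expected conceptions under the assumed rates. The case for acting therefore rests on the low cost of the remedy.

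**What to change.** Reconcile Appendix A with Section 6.3.1 by marking the serum pregnancy test at follow-up Week 13 for women under footnote m. Run it on blood already taken there: chemistry, hematology, lipid panel, PK and antibody samples are all scheduled at that visit. The contraception period is unchanged. If the blank is deliberate, the protocol should give the reason.

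The cost is one added mark in the table and one extra assay per woman concerned. The sponsor has already filled an omission in Appendix A, the skinfold measurements, by administrative clarification letter. The remedy is partial: under the assumed lags, conceptions in roughly the last 0 to 7 protected days would still be missed at the nominal visit day, against 35 to 42 days now. Section 9.5.4 should stay as it is to cover that remainder.

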# Subjects on stable diet known to the investigator and followed at the site may go from Screening to qualification without the diet run-in period.

† Qual =Qualification

ISIS 703802-CS5

All procedures and study samples are to be done pre-dose at respective visits, unless specified

- a Full physical exam will be performed at the screening visit and an abbreviated physical exam will be performed during treatment and follow-up periods.
- b Height only required at Screening
- c Mixed Meal Test-refer to Appendix E for further details
- d MRI and DEXA scan will only be performed during Screening after all other eligibility criteria are met. MRI should be performed 10 days (+/- 2 days) prior to anticipated Day 1 date to allow time for result reporting and analysis. DEXA scan should be performed as close to anticipated Day 1 date as possible.
- e All tests listed in Appendix B under Extended Urinalysis should be performed, including routine urinalysis, urine microscopy, UACR and UPCR.
- f Assessments and procedures to be conducted by either a home healthcare service or the Study Center. Subject Study Center visits must be no more than 4 weeks apart during the treatment period.
- g Urine samples for renal biomarkers will be collected. Sample analysis will be conducted in accordance with Safety Monitoring for Renal Function (Section 8.5.2).
- h During follow-up period, hematology sampling for platelet values are taken every 14 days (+/- 2 days) for 6 weeks after last dose of Study Drug, then at Week 8 and Week 13 Follow-up visits.
- i Serum Creatinine and Cys-C will be collected as a part of chemistry panel at visits when chemistry panel is performed, or as stand-alone samples at time points when a chemistry panel is not performed.
- j Blood samples to be collected after an overnight fast of at least 10 hours and preferably not more than 12 hours, unless tests are repeated for safety reasons.
- k If the platelet value, serum creatinine or liver enzyme tests are uninterpretable (e.g., due to clumping, hemolysis or quantity not sufficient) a repeat blood specimen should be re-drawn as soon as possible (ideally within 7 days). All platelet count results will be reviewed promptly (within 48 hours of receipt) by the Investigator as per Section 6.2.1. Any case of a platelet count ≤ 50,000/mm^3 should be reported in an expedited fashion to the Sponsor.
- Refer to Appendix C for PK Sampling schedule.
- m Women who are not surgically sterile or post-menopausal.
- n Serum and plasma samples will be collected and stored for follow-up exploration of laboratory findings and/or AEs (e.g., measurement of cytokine and/or chemokine levels, measurement of additional markers of kidney function, measurement of antibodies, etc.) and will be retained until completion of the final study report.
- o Treatment period is defined as the time from the first dose through one dosing interval post last dose.
- p Genetic testing will only be performed for eligibility if there is no documented genetic testing in medical history.
- q 24-hour urine sample for creatinine clearance and protein should also be obtained in the event of an eGFR (CKD-EPI) value meeting criteria specified in Sections 8.5.2 and 8.6.2.

Time (time is in reference to Study Drug administration):

1 Pre-dose

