### 3.4 Overall Study Duration and Follow-up

The length of subjects' participation in the study may be up to 45 weeks. This includes an up to 5-week screening period, that includes a 4-week diet stabilization / run-in period, a 1-week qualification period, a 26-week treatment period, and a 13-week post-treatment evaluation period.

Subjects may be required to attend additional visits for monitoring of adverse events or abnormal investigation results. The frequency of additional monitoring will be determined by the Study Medical Monitor in consultation with the Investigator.

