## **3.4 Overall Study Duration and Follow-up**

The length of subjects' participation in the study may be up to 45 weeks. This includes an up to 6-week screening period, that includes a 4-week diet stabilization / run-in period, a 2-week qualification period, a 26-week treatment period, and a 13-week post-treatment evaluation period.

Subjects may be required to attend additional visits for monitoring of adverse events or abnormal investigation results. The frequency of additional monitoring will be determined by the Study Medical Monitor in consultation with the Investigator.

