# 3.4.1 Screening/Qualification

Subject eligibility for the study will be determined within 42 days/6 weeks prior to study entry. Potential subjects will report to the Study Center for screening assessments at specified intervals within the 6-week screening period as detailed in the Schedule of Procedures in Appendix A. As part of the screening period, subjects will have a 4-week diet stabilization/run-in period followed by a up to 2-week qualification period. Subjects on stable diet known to the investigator and followed at the site may go from Screening to qualification without a 4-week diet run-in. At the qualification visit TGs will be measured. A baseline DEXA scan and MRI will be obtained to assess liver fat content once all other eligibility has been confirmed. MRI results must be available prior to registration and administration of the first dose of study drug.

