# MINOR Criteria

- a. Requirement for high doses of insulin, e.g., requiring  $\geq$  200 U/day,  $\geq$  2 U/kg/day, or currently taking U-500 insulin
- b. Presence of acanthosis nigricans on physical examination

- c. Evidence/history of polycystic ovary syndrome (PCOS) or PCOS-like symptoms (hirsutism, oligomenorrhea, and/or polycystic ovaries)
- d. History of pancreatitis associated with hypertriglyceridemia
- e. Evidence of non-alcoholic fatty liver disease
  - Hepatomegaly and/or elevated transaminases in the absence of a known cause of liver disease or radiographic evidence of hepatic steatosis (e.g., on ultrasound or CT)
- 4. A diagnosis of diabetes mellitus, made at least 6 months prior to the Screening, and:
  - A HbA1c  $\geq$  7% to  $\leq$  12% at Screening,
  - On anti-diabetic therapy consisting of:
    - a. Metformin  $\geq$  1500 mg/day, or
    - b. If the dose of metformin is < 1500 mg/day, or metformin is not tolerated, then the patient should be on other oral anti-diabetic drugs (OAD) or an injectable glucagon-like peptide-1 (GLP-1) receptor agonist, or
    - c. Insulin therapy alone or in combination with other anti-diabetic drugs
- 5. Hypertriglyceridemia as defined by Fasting TG levels ≥ 500 mg/dL (≥ 5.7 mmol/L) at both Screening and Qualification visits. Patients with the clinical diagnosis of FPL and with Fasting TG levels ≥ 200 (≥ 2.26 mmol/L) to < 500 mg/dL (≥ 5.7 mmol/L) at both Screening and Qualification Visits who meet the genetic or family history criteria for study inclusion may be further screened and enrolled in the study

- 6. Presence of hepatosteatosis (fatty liver), as evidenced by a Screening MRI indicating a hepatic fat fraction (HFF) ≥ 6.4%
- 7. Willing to maintain their customary physical activity level and to follow a diet moderate in carbohydrates and fats with a focus on complex carbohydrates and replacing saturated for unsaturated fats

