# 5.2 Exclusion Criteria

- 1. A diagnosis of generalized lipodystrophy
- 2. A diagnosis of acquired partial lipodystrophy (APL)
- 3. Acute pancreatitis within 4 weeks of Screening
- 4. History within 6 months of Screening of acute or unstable cardiac ischemia (myocardial infarction, acute coronary syndrome, new onset angina), stroke, transient ischemic attack, or unstable congestive heart failure requiring a change in medication
- 5. Major surgery within 3 months of Screening
- 6. History of heart failure with New York Heart Association functional classification (NYHA) greater than Class II
- 7. Uncontrolled hypertension (blood pressure [BP] > 160 mm Hg systolic and/or 100 mm Hg diastolic)
- 8. Clinically-significant abnormalities in screening laboratory values that would render a subject unsuitable for inclusion, including the following:
  - a. Urine protein/creatinine ratio (UPCR)  $\ge 0.25$  mg/mg. In the event of a UPCR above this threshold, eligibility may be confirmed by a quantitative total urine protein measurement of < 1 g/24-hr
  - b. Estimated GFR < 60 mL/min/1.73 m^2 (as determined by the Chronic Kidney Disease-Epidemiological Collaboration (CKD-EPI) Equation
  - c. Alanine aminotransferase (ALT) or aspartate aminotransferase (AST) > 2x ULN
  - d. Bilirubin > ULN, unless prior diagnosis and documentation of Gilbert's syndrome in which case total bilirubin must be  $\leq 3 \text{ mg/dL}$

- e. Alkaline phosphatase (ALP) > 1.5 X ULN
- f. Platelet count < LLN
- 9. Uncontrolled hyper- or hypothyroidism. Subjects on dose stable replacement therapy for at least 3 months prior to Screening will be allowed
- 10. History within 6 months of Screening of drug or alcohol abuse
- 11. History of bleeding diathesis or coagulopathy or clinically-significant abnormality in coagulation parameters at Screening
- 12. Active infection requiring systemic antiviral or antimicrobial therapy that will not be completed prior to Study Day 1
- 13. Known history of or positive test for human immunodeficiency virus (HIV), hepatitis C or chronic hepatitis B
- 14. Malignancy within 5 years, except for basal or squamous cell carcinoma of the skin or carcinoma *in situ* of the cervix that has been successfully treated
- 15. Treatment with another investigational drug, biological agent, or device within 1-month of Screening, or 5 half-lives of investigational agent, whichever is longer
- 16. Unwilling to comply with lifestyle requirements (see Section 6.3)

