# Appendix A Schedule of Procedures

	Scree	ning				Treat	ment Deries	1			Falls		riad
	Run-in #	Qual †				Treatr	ment Period	1			Folic	ow-up Pe	rioa
Study Week	-6 to -1	-1 to 0	1	5	9	13	17	21	25	27/ET	4*	8*	13*
Study Day	-42 to -1	-7 to -1	1	29	57	85	113	141	169	183	*Weeks from the end of treatment period o		
Visit and Testing Window +/- Days	0	0	0	2	2	2	3	3	3	0	3	3	3
Informed Consent	Х												
Outpatient Visit	Х	Х	Х	Х	Х	Х	Х	Х	Х	Х	Х	Х	Х
Inclusion/Exclusion Criteria	Х	Х	Х										
Medical History	Х												
Genetic Testing p	Х												
Vital Signs	Х		Х	Х	Х	Х	Х	Х	Х	Х	Х	Х	Х
Physical Examination a	Х		Х	Х		Х				Х	Х		Х
Body Weight and Height b	Х	Х	Х	Х	Х	Х	Х	Х	Х	Х	Х	Х	Х
Waist and hip circumference	Х									Х			
DEXA Scan	Xď					Х				Х			
12- lead ECG (triplicate)	Х		Х	Х		Х		Х		Х	Х	Х	Х
Ultrasound	Х												
Mixed Meal Test c		Х				Х				Х			
MRI	Xď	-				Х				Х			
24-Hour Urine for Creatinine Clearance and Protein q		Х											
Extended Urinalysis e	Х		EV	ERY 14 DA	YS (+/- 2 d	ays) e, f	Х	Х	Х	Х	Х	Х	Х
Serum Creatinine and Cys-C i, j, k	Х		EV	ERY 14 DA	YS (+/- 2 d	ays) f, i	Х	Х	Х	Х	Х	Х	Х
Chemistry Panel j, k	Х		E١	/ERY 14 D/	4YS (+/- 2 c	days) f	Х	Х	Х	Х	Х	Х	Х

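### Does the MRI day in footnote d of Appendix A conflict with the later Qualification triglyceride test in a way that needs an amendment?

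*Combined protocol and SAP*

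**What the plan says.** All text here is from Amendment 1 unless noted.

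- **MRI condition and day.** Footnote d of Appendix A states that "MRI and DEXA scan will only be performed during Screening after all other eligibility criteria are met", and that "MRI should be performed 10 days (+/- 2 days) prior to anticipated Day 1 date to allow time for result reporting and analysis". Section 6.2.6 repeats the condition without the day count.
- **Qualification TG.** Inclusion criterion 5 (Section 5.1) sets a TG threshold to be met "at both Screening and Qualification visits". Section 6.1.1 has TG measured at the qualification visit. Appendix A prints that visit at Study Day -7 to -1 with a window of 0 days.
- **24-hour urine.** The row "24-Hour Urine for Creatinine Clearance and Protein" has its only screening-phase mark, as the table is reproduced, in the Qualification column. Exclusion criterion 8a (Section 5.2) says that after a high urine protein/creatinine ratio "eligibility may be confirmed by a quantitative total urine protein measurement of < 1 g/24-hr".
- **Length of qualification.** Section 3.4 lists "a 4-week diet stabilization / run-in period, a 2-week qualification period". Section 3.4.1 has the run-in "followed by a up to 2-week qualification period". Section 3.4 of the original protocol had "a 1-week qualification period".
- **Safeguard.** The synopsis (Study Visit Schedule and Procedures) requires both the TG and the MRI results before registration and first dose.

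**The concern.** A condition that the MRI must follow every other eligibility check cannot be met if one of those checks is scheduled after the MRI. A site that follows the advised MRI day scans before the Qualification TG is known. A site that waits for a TG drawn in the printed column has at most 7 days left to Day 1, against the 8 to 12 days that footnote d sets aside for reading and reporting. On a literal reading every enrolled subject departs from one of the two texts.

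The 24-hour urine seems to add a second late eligibility result, and the 7-day column seems to contradict the two weeks in Section 3.4. At stake would be protocol deviations, scans in subjects who then fail screening and, at worst, doubt about whether subjects were eligible when treated.

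**Working it through.** **1. The plan's own duration.** Section 3.4 gives up to 45 weeks. Run-in 4 + qualification 2 + treatment 26 + follow-up 13 = 45, so the figure reproduces. With a 1-week qualification the sum is 44. The two weeks in Section 3.4 are therefore deliberate.

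**2. The windows.**

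| Item | Source | Study days |
|---|---|---|
| MRI, 10 ± 2 days before Day 1 | Footnote d | -12 to -8 (5 days) |
| Qualification visit, with TG | Appendix A | -7 to -1 (7 days) |
| Two-week qualification period | Sections 3.4, 3.4.1 | -14 to -1 (14 days) |

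The first two share 0 days. Of the 7 × 5 = 35 pairs of TG day and MRI day, none has the MRI on or after the TG draw. If a Day 0 is counted, the MRI window becomes Day -11 to -7; the one shared day is Day -7, usable only with a same-day TG result.

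Over the full two weeks there are 14 × 5 = 70 pairs. Those with TG first number 25, 20, 15 and 10 for a TG reporting time of 0, 1, 2 and 3 days. The reporting time is an assumption, because the documents give none. Both orders therefore fit inside the two-week period; only the printed column rules out TG first.

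**3. Is the 7-day column itself a conflict?** A visit window can lie inside a longer period, and Section 3.4.1 sets two weeks as a maximum. The original protocol already paired an upper limit of two weeks in Section 3.4.1 with the same Day -7 to -1 column. Amendment 1 brought Section 3.4 into line with Section 3.4.1. Nothing is breached.

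**4. Is the 24-hour urine a second conflict?** Only conditionally. Criterion 8 concerns screening laboratory values, and the 24-hour protein matters for 8a only when the ratio is at or above 0.25 mg/mg. Nothing ties that follow-up test to the Qualification column, and Section 6.1.1 allows safety laboratory re-tests for eligibility. The collection scheduled for every subject may instead supply the baseline creatinine clearance used in Section 8.6.2. TG is the only firm mismatch.

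**5. Can the condition be fully literal?** No. Exclusion criteria 12 and 17c, d, g, i and k run up to Day 1 or to dosing, so some criteria cannot be settled 8 to 12 days earlier whatever happens to TG. The synopsis describes a workable order: Screening criteria and a qualifying MRI, with TG measured in addition at qualification.

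**6. What could go wrong in numbers?** Only a scan in a subject who then fails Qualification TG. If a fraction p of those scanned fails, enrolling n subjects costs about n·p/(1-p) such scans. The documents do not give p. Assume lognormal TG, within-subject CV of 15% to 35%, and no diet effect.

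- Spread and centre from the published quartiles in Section 2.1 (232/856 and 279/801 mg/dL): p is about 8% to 21% at the 500 mg/dL threshold and 3% to 7% at 200 mg/dL.
- The second set of quartiles implies a median of √(279 × 801) ≈ 473 mg/dL, but the cited median is 342. Re-centred on 342 with the same spread, p is about 12% to 28% at 500 and 5% to 10% at 200.

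Over the whole range, n = 3 with p = 3% gives 3 × 0.03/0.97 ≈ 0.1 scans, and n = 6 with p = 28% gives 6 × 0.28/0.72 ≈ 2.3. The upper end puts all six subjects on the 500 mg/dL threshold, although criterion 5 opens a 200 mg/dL route for genetic or family-history cases.

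**7. Effect on the analysis.** Section 10.4 averages the Day 1 pre-dose lipid value with the last earlier one, and takes the last pre-dose value for other measures, including liver fat. Neither definition depends on whether MRI or TG came first.

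**The case for a change.** The case for a change is that the condition is firmly worded and repeated in the synopsis and in Sections 3.1, 3.4.1, 6.1.1 and 6.2.6, so it is not a stray phrase. Section 6.1.1 places final eligibility assessments at the qualification visit, which does not sit easily with the synopsis. The source looks like an incomplete edit: Amendment 1 introduced the MRI day and the stricter condition but left the Study Day row alone. A text edit is cheap and would give sites and monitors one rule.

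The dates and the origin stand. The benefit does not. Letting TG follow the MRI keeps the same visits and scans, and the same expected number of scans in later TG failures. It would also largely restore the condition in the original footnote d, initial screening eligibility, which Amendment 1 replaced with an explicit rationale. Because the same sentence governs DEXA, it would loosen that condition too, although a DEXA done close to Day 1 can follow the Qualification TG as printed.

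Moving TG ahead of the MRI could avoid the 0.1 to 2.3 scans, but the Qualification visit would have to move earlier, with its lipid sample, mixed meal test and quality-of-life assessment. That is a choice of logistics for the sponsor; no statistical reason favours it. The claim that every subject departs from the plan is also too strong, since the MRI day is advisory and the condition cannot be literal.

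**Conclusion.** The mismatch between footnote d and the Qualification TG is real: 0 shared days as printed. It is a clerical slip whose correction would gain nothing for the trial's results. The requirement that TG and MRI results both precede registration and first dose is clear and does not depend on their order. The baselines, the primary TG endpoint, the liver fat endpoint and the safety summaries are unchanged. The 24-hour urine is at most a conditional conflict, and the 7-day column is compatible with a qualification period of up to two weeks.

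What remains is minor deviations and perhaps 0.1 to 2.3 scans in later TG failures, a rough range that rests on an assumed within-subject CV and a lognormal fit. The conclusion does not depend on that range, only on the registration safeguard being followed. No change to the plan is called for.
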